3.5.3 Efficacy assessments

3.5.3.1 Laboratory evaluations

In general UFC is determined by collecting two or three 24-hour urine samples and calculating the mean. However routine site procedures may also only foresee one single urine sample to assess UFC. The frequency of UFC determination will probably vary from the initiation of treatment (when UFC values will be performed more frequently than at monthly interval) as compared to the time after obtaining control.

After obtaining control, at a minimum UFC assessments are recommended to be collected every 6 months.

In addition, the last available UFC value before study entry will be collected on the CRF, only if there is no UFC value available at baseline.

Other biochemical measures of disease activity that will be collected as available in addition to UFC in this study include serum cortisol, serum cortisol after dexamethasone testing, salivary cortisol, plasma ACTH, and fasting serum lipid profile.

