The data will be summarized with respect to demographic and baseline characteristics, safety observations and measurements as well as efficacy assessments. Data will be summarized and displayed by time intervals based visit windows rather than by a strict visit schedule, in order to reflect the nature of this study. Details on definition of time windows will be provided in the Report and Analysis Plan (RAP). Furthermore, for patients who discontinue treatment prior to the 3-year observation period, their safety and efficacy parameters will be reported according to the time window that corresponds to 90 days from the Day of last dose of pasireotide s.c. Continuous variables will be summarized by number of patients, mean, standard deviation, minimum, median and maximum. Categorical variables will be summarized by absolute and relative frequencies. Counts of missing values for both continuous and categorical variables will be reported. Results with and without imputation will be reported.

Baseline assessment refers to the last assessment prior to the patient's first pasireotide s.c. dose recorded after the signing of the informed consent or acknowledging an equivalent document (e.g., written information) as per country regulation. For some assessment this definition maybe expanded to include the first assessment post the first pasireotide s.c. dose recorded after informed consent or an equivalent document (e.g., written information) as per country regulation.

In this study, the first analysis will occur at about 12 months after the first patient enters the study. After this first analysis there will be one analysis on a yearly basis. The final analysis will occur when all patients complete the study. The same analysis will be performed for all analyses time points.

Assessment time points are considered relative to first pasireotide s.c. dose recorded on or after the singing of the informed consent or acknowledging of an equivalent document (e.g., written information) as per country regulation, unless noted otherwise.

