6.5.1.5 Handling of missing data

For the analysis of these efficacy endpoints, for missing values, Mixed Effects Repeated Measured Model will be employed to assess the longitudinal changes in efficacy parameters. In addition, sensitivity analyses will be performed to assess the robustness of the efficacy findings.

The imputation method as well as sensitivity analyses will be specified in the RAP.

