#### 8.2.1 Secondary efficacy endpoints

The secondary efficacy endpoints are as follows:

---

1. Proportion of patients with a mean UFC  $\leq$  ULN at 1, 3, 6, 12, 24 and 36 months after enrollment into the study.
2. The absolute and percentage change from baseline in biochemical measures of disease activity (mean UFC, serum cortisol, serum cortisol after dexamethasone, salivary cortisol, ACTH, fasting serum lipid profile (total cholesterol, HDL, LDL)) over time.
3. Proportion of patients achieving normalization of biochemical measures of disease activity (serum cortisol, serum cortisol after dexamethasone, salivary cortisol, ACTH) over time, where normalization refers to being within the upper and lower limit of normal ranges.
4. The absolute and percentage change from baseline in clinical signs and symptoms (blood pressure, body weight, body mass index, waist circumference) over time.
5. The proportion of patients with favorable shift from baseline in clinical symptoms of Cushing's disease over time.
6. The change from the last dose of pasireotide s.c. to 90 days after permanent discontinuation of pasireotide s.c. for patients who discontinue pasireotide s.c. prior to completing 3-year observation period. This change will be evaluated for all available continuous efficacy parameters.
7. The absolute and percentage change from baseline in tumor size over time.
8. The absolute and percentage change from baseline in patient reported outcome questionnaires (Cushing QoL and EURO QoL) over time.

All efficacy analyses will be done for all patients in the FAS and for the two cohorts. And all efficacy analyses except those under 5 will be done for the subgroup patients from German sites. Additionally, the efficacy analyses described under 1, 2, and 3 above will be repeated for the following subgroups of patients:

- Patients treated with monotherapy pasireotide s.c. throughout the study
- Patients treated with a combination of pasireotide s.c. with any other therapy for Cushing's disease throughout the study
- Patients who switched from monotherapy to combination therapy or vice versa at any time during the study

For all continuous efficacy variables (biochemical measures of disease activity, blood pressure, body weight, body mass index, waist circumference, tumor size), a Mixed Effects Repeated Measures Model will also be employed to assess the longitudinal changes in these variables.

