Except for the analysis of change from end of treatment to 90 days later, the efficacy analyses will only consider on-treatment values, defined as values assessed before end of treatment + 3 days.

All assessments will be assigned to time windows based on the study day on which the assessment was performed. If there are multiple values within a time window, the assessment closest to the target day of the time window will be used, if not indicated otherwise. Further details including the start and end days of the time windows are available in Appendix 16.1.9 of the CSR.

The continuous efficacy parameters will be also evaluated through a couple of sensitivity analyses: the first will be imputing the worst value at that time window in case of missing data and the second on the patients with the full set of values. The same Mixed Model will be employed for both the analyses.

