### **8.2.1.1 Proportion of patients with mean UFC $\leq$ ULN**

Analysis of all patients

In general, UFC is determined by collecting two or three 24-hour urine samples and calculating the mean of the 24-hour UFC values. However, routinely some sites may also use only one single 24-hour urine sample to assess UFC. Therefore in this study, mean UFC (mUFC) refers to the mean if more than one 24-hour UFC value was reported within 2 weeks and to the single value if only one value was reported.

If a 24-hour urine collection was performed but 24-hour UFC was not documented, 24-hour UFC will be calculated as product of 'urinary cortisol, random' (concentration of cortisol in 24-hour urine) and the total volume of 24-hour urine, if available.

For each time window (Month 1, 3, 6, 9, 12, 18, 24, 30 and 36), the number and proportion of patients with mean UFC (mUFC)  $\leq$  ULN will be presented together with corresponding exact (Clopper-Pearson) 95% confidence intervals (CI) for the proportions. The proportion will be calculated relative to the number of patients with a value for the respective time point (mUFC and ULN).

In addition, the number of patients without mUFC value and the number of patients with missing ULN (but mUFC value available) will be displayed by time window. In each time window, only those patients will be included who were treated during that window and followed up until the end of the respective time window.

Analysis of patients who discontinued pasireotide s.c.

A similar analysis will be performed for the subgroup of patients who discontinued pasireotide s.c. prematurely and had an assessment on-treatment and 90 days after last dose. The statistics described above will be displayed for the patient's last value on treatment and for the last value assessed during the 90 days after last dose. Furthermore, the status of the last mUFC value on treatment ( $\leq$  ULN,  $>$  ULN) will be cross-tabulated against the status 90 days after last dose.

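### The mUFC control rate has only an observed-case analysis, and the quality-of-life scores are not named in the mixed model, although the protocol commits to imputation and sensitivity analyses for the efficacy endpoints

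*SAP*

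**What the plan says.** **Protocol.** The opening text of section 6 states: "Results with and without imputation will be reported". Section 6.5.1.5, which covers the efficacy endpoints listed in 6.5.1, calls for a mixed model to deal with missing values and adds: "In addition, sensitivity analyses will be performed to assess the robustness of the efficacy findings". It leaves the imputation method and the sensitivity analyses to the report analysis plan. The list in 6.5.1 begins with the mUFC proportion and ends with Cushing QoL and EURO QoL.

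On measurement frequency, Protocol 3.5.3.1 expects UFC to be taken at a different rate once control is reached, and sets a floor: "After obtaining control, at a minimum UFC assessments are recommended to be collected every 6 months". Table 3-1, footnote 5, suggests monthly UFC for three months and 3-monthly thereafter, with no distinction by control status.

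**SAP.** Section 8.2.1.1 sets the denominator: "The proportion will be calculated relative to the number of patients with a value for the respective time point (mUFC and ULN". It restricts each window further: "In each time window, only those patients will be included who were treated during that window and followed up until the end". Missing data are displayed as "the number of patients without mUFC value and the number of patients with missing ULN", by window. Section 8.2.1 gives the scope of the mixed model in a parenthesis that ends "body mass index, waist circumference, tumor size), a Mixed Effects Repeated Measures Model will also be employed to assess the longitudinal changes"; no quality-of-life score is in it. The sensitivity analyses (worst-value imputation and complete cases, both with the same mixed model) are introduced by: "The continuous efficacy parameters will be also evaluated through a couple of sensitivity analyses". Section 8.2.1.7 gives the quality-of-life scores descriptive statistics and median confidence intervals. Section 4.1 repeats most of the protocol's summary paragraph without its sentence on imputation, and section 3 reports no change to the planned analysis.

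**The concern.** The protocol left the missing-data method to the analysis plan; it did not waive it. For the responder rate the plan supplies none, and for the quality-of-life scores it is at best unclear whether it supplies one.

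This matters for the control rate because having a value can depend on the outcome. A controlled patient who is measured 6-monthly can pass through a shorter window without a UFC and drop out of that window's denominator, while an uncontrolled patient under closer watch stays in. The windows in SAP Table 6-2 are short up to Month 12 and about six months long from Month 18. A constant control rate could therefore appear to rise over time, in a study meant to document short- and long-term efficacy. Separately, patients who stop treatment leave the later denominators. That may raise the late rates, because those who remain are likely to be the ones doing well. No planned analysis bounds either effect.

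**Working it through.** No figure in the documents rests on this point, so there is none to reproduce. The following sizes the mechanism under stated assumptions.

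**Step 1: window lengths** (SAP Table 6-2, end day minus start day plus 1). Month 6: 229 - 137 + 1 = 93. Month 9: 320 - 230 + 1 = 91. Month 12: 458 - 321 + 1 = 138. Month 18: 641 - 459 + 1 = 183. Month 24: 821 - 642 + 1 = 180. Months 30 and 36: 184 and 182.

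**Step 2: chance c that a controlled patient has a value in the window.** With one measurement every 6 x 30.4375 = 182.625 days at random phase, c = min(1, length / 182.625).
- Month 6: 93 / 182.625 = 0.51
- Month 9: 91 / 182.625 = 0.50
- Month 12: 138 / 182.625 = 0.76
- Months 18 to 36: 0.99 to 1.00

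With 3-monthly measurement (91.3 days), c is about 1.00 in every window from Month 6.

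**Step 3: observed-case rate.** Let p be the true control rate among treated patients and assume every uncontrolled patient has a value. Then observed = p c / (p c + 1 - p). For p = 0.263 at Month 6: 0.263 x 0.509 = 0.134, and 0.134 / (0.134 + 0.737) = 15.4%.

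| True rate p | Month 6 | Month 9 | Month 12 | Month 24 |
|---|---|---|---|---|
| 14.6% | 8.0% | 7.9% | 11.4% | 14.4% |
| 26.3% | 15.4% | 15.1% | 21.2% | 26.0% |
| 40% | 25.3% | 24.9% | 33.5% | 39.7% |
| 50% | 33.7% | 33.3% | 43.0% | 49.6% |

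The first two rates are the phase III response rates in Protocol section 1, which used a stricter definition (no up-titration). The 40% and 50% rows are assumptions. At 26.3%, 40% and 50% the shortfalls at Months 6 and 9 are about 11, 15 and 16 to 17 points; at Month 12 they are 5.1, 6.5 and 7.0.

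Month 3 is left out because the suggested monthly UFC over the first three months makes a 6-monthly schedule doubtful there. The formula alone (76 days, c = 0.42) would give 29% against a true 50%, a gap of about 21 points.

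**Step 4: what bounds would show.** Take 100 treated patients, 26 controlled, with measurement probabilities 0.5 (controlled) and 0.9 (uncontrolled). Observed cases give 13/80 = 16% (exact 95% CI 8.9 to 26.2). Counting the 20 missing as uncontrolled gives 13/100 = 13%; counting them as controlled gives 33/100 = 33%. The bounds enclose the true 26%. With equal measurement at 0.9 in both groups the observed rate is 23/90 = 25.6%, close to the truth.

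**Step 5: leaving out discontinued patients.** If 50 of 100 have stopped by a late window and 70% of the rest are controlled, the planned rate is 35/50 = 70%, against 35/100 = 35% on the full analysis set. With 30 or 70 stopped, the full-set figures are 49% and 21%. The stopping rates and the 70% are assumptions.

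**The case against.** A reader might infer that the early control rates are biased downward and that any rise after Month 12 is an artefact. The documents do not support that. Protocol 3.5.3.1 says only that frequency will probably vary, six months is a minimum, and Table 3-1 suggests 3-monthly UFC for everyone after month 3. At that frequency the calculated bias vanishes. Random phase is also assumed. Measurements on 6-monthly anniversaries (days 183, 365, 731, 1096) fall inside the Month 6, 12, 24 and 36 windows and leave no bias there, although other phases, such as days 91 and 274, miss the Month 6 window altogether. A patient who first reaches control within a window has a value in it by construction. This part of the objection stands: the bias is possible, not shown.

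A reader might also infer that missing UFC data are ignored. They are not. The missing counts by window would let a reader work out crude bounds; discontinued patients with both an on-treatment and a follow-up value get a separate table; and continuous mUFC has a mixed model, worst-value imputation and a complete-case analysis. Protocol 6.5.1.1 itself asks only for number, percentage and exact interval. But none of these is an imputed or model-based control rate, and 6.5.1.5 makes no exception for the proportion.

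A third tempting inference is that quality of life is definitely excluded from the sensitivity analyses. The sentence that introduces them speaks of continuous efficacy parameters in general and could include the scores. Only the mixed-model list clearly leaves them out.

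Finally, these are secondary, descriptive endpoints in an exploratory study whose primary objective is safety. That limits the severity but does not remove the commitment.

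**Conclusion.** The gap between the documents is firm for the mUFC proportion: the protocol commits to imputed results and sensitivity analyses, the SAP gives an observed-case rate with missing counts, and section 3 declares no change. For Cushing QoL, the EQ-5D index and the EQ VAS, the omission from the mixed-model list is clear, while their place in the sensitivity analyses is ambiguous.

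The numerical consequence is conditional. Selective measurement could lower the control rate at Months 6 and 9 by anything from zero to about 17 points for true rates up to 50%, by up to 7 points at Month 12, and hardly at all from Month 18. The upper figures need every controlled patient to be at the 6-monthly floor at random phase and every uncontrolled patient to be measured in each window. Leaving out discontinued patients may work the other way in late windows. Its size depends on a drop-out rate that the documents do not give, and an on-treatment rate also answers a different question from one on all enrolled patients. No size can be put on the quality-of-life part. The point should be dealt with, but it does not touch the primary endpoint.

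**What to change.** In SAP 8.2.1.1, keep the observed-case rate and report beside it, by window:

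- (a) two bounds for patients on treatment in the window, with missing mUFC status counted as uncontrolled and then as controlled;
- (b) a rate on the full analysis set denominator, with discontinued patients counted as not controlled;
- (c) a model-based marginal proportion that uses all windows, for example by multiple imputation of mUFC or by a repeated-measures logistic model with marginal standardisation. The standardisation is needed because a logistic mixed model gives subject-specific estimates, not the proportion that 8.2.1.1 reports.

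In SAP 8.2.1, name the Cushing QoL score, EQ-5D index and EQ VAS in both the mixed-model list and the sensitivity-analysis text, using the Table 6-3 windows. Record in SAP section 3 any departure from Protocol 6 and 6.5.1.5 that remains.

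The cost is SAP wording and some extra runs on data already being collected, with no burden on sites or patients.

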### 4.2 *Patient disposition, demographics and other baseline characteristics*

#### 4.2.1 Patient disposition

Frequency distributions will be used to summarize the patient disposition at the time of analysis (treatment ongoing, treatment completed, treatment discontinued prematurely, study ongoing, study completed, study discontinued prematurely) and associated reasons for discontinuation of study medication and study using the FAS and the subgroup of patients from German sites. The follow-up time, i.e. the patient's time in the study (in months), will be summarized with descriptive statistics.

All data collected at baseline such as the history of Cushing's disease (time since diagnosis in months, status of disease, prior pituitary surgery/irradiation, time since last prior pituitary surgery/irradiation, duration of prior treatment with pasireotide, baseline symptoms), will be summarized using descriptive statistics and will be listed as required. This summary will be prepared for the FAS and the subgroup of patients from German sites.

---

The duration of prior treatment with pasireotide (in months) will be summarized with descriptive statistics, as continuous variable and by category (<=3 months, >3 to 6 months, >6 to 12 months, >12 months). The number and percentage of patients who used pasireotide as single therapy and of those who used it as combination therapy will be presented. This summary will be prepared for the FAS and the subgroup of patients from German sites.

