### 6.1.5 Study day

Study days are calculated relative to the date of first dose during the study. The date of first dose defines Day 1. Day -1 is one day before Day 1, Day -2 two days before Day 1, Day 2 one day after Day 1, and so on. That is, there is no Day 0.

More specifically, the study day is calculated as

study day = (date of assessment/event - date of first dose) + 1

if the assessment or event is on or after the date of first dose, and as

study day = (date of assessment/event - date of first dose)

otherwise.

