### **8.2.1.2 Absolute and percentage change from baseline in biochemical measures of disease activity**

For each time window (Month 1, 3, 6, 9, 12, 18, 24, 30, 36), observed values and, the absolute and percentage change from baseline in biochemical measures of disease activity (mean UFC, serum cortisol, serum cortisol after dexamethasone, salivary cortisol, ACTH, fasting serum lipid profile (total cholesterol, HDL, LDL) will be summarized with descriptive statistics. Distribution-free 95% CIs will be given for the median changes.

Furthermore, the time course of these parameters will be displayed graphically using box-plots.

In addition, the absolute and percentage change from the last assessment while on pasireotide s.c. to the last value during the 90-days follow-up period will be summarized in a similar manner.

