### **8.2.1.3 Proportion of patients with normalization of biochemical measures of disease activity**

This analysis will be done for serum cortisol, serum cortisol after dexamethasone, salivary cortisol, ACTH.

For each time window, the number and percentage of patients with normalization of biochemical measures of disease activity will be presented together with corresponding exact

(Clopper-Pearson) 95% CI. For this analysis, a patient is considered to have achieved normalization within a time window if all measurements taken within this window are within the normal range. The proportion will be calculated relative to the number of patients with a value for the respective time point.

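### The follow-up condition in SAP 8.2.1.1 cannot be met at Month 36 by a patient who completes the study exactly on plan, and the SAP neither gives an exception nor says which statistic the condition restricts

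*SAP*

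**What the plan says.** SAP 8.2.1.1 presents the number and proportion of patients with mUFC at or below ULN in each window from Month 1 to Month 36. It sets the denominator first: "The proportion will be calculated relative to the number of patients with a value for the respective time point (mUFC and ULN"). A new paragraph then adds, by window, "the number of patients without mUFC value and the number of patients with missing ULN" where an mUFC exists. That paragraph closes by saying that in each window "only those patients will be included who were treated during that window and followed up until the end of the respective time window". It does not say what these patients are included in.

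Other places that bear on the point:

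- **SAP Table 6-2:** Month 36 has target Day 1096, start Day 1006 and end Day 1187. A further window, After Month 36, opens on Day 1188 with no upper limit.
- **SAP 6.1.5:** "Study days are calculated relative to the date of first dose during the study".
- **Protocol 3.1 and 3.1.2:** each patient is followed for 3 years from enrollment, and efficacy data for completers stop at the last follow-up visit. Patients who stop pasireotide s.c. early are followed for 3 months after the last dose.
- **Protocol 3.5.2.2:** serious adverse events are reported until 28 days after the 3-year period is completed.
- **SAP 8.2.1:** "the efficacy analyses will only consider on-treatment values, defined as values assessed before end of treatment + 3 days".
- **SAP 4.2.1:** "The follow-up time, i.e. the patient's time in the study (in months), will be summarized with descriptive statistics".
- **SAP 8.2.1.3**, on normalization of other biochemical measures: "The proportion will be calculated relative to the number of patients with a value for the respective time point". It has no follow-up condition, and neither does Protocol 6.5.1.1 for the mUFC proportion itself.

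**The concern.** Month 36 is the last time point named in this secondary endpoint, and the final report is where it will be fully populated. The inclusion rule asks for follow-up to a day that lies beyond the planned end of the study for every patient. The consequence depends on what the sentence restricts:

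- **Missing counts only.** The proportion stands. However, a completer with no Month 36 mUFC is not counted as missing, so the table understates how incomplete the Month 36 data are among the patients who stayed to the end.
- **The whole table.** On-plan completers also leave the Month 36 proportion, and the patients who remain are selected on having been seen beyond plan.

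Two programmers could follow the text in good faith and produce different Month 36 tables.

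**Working it through.** **1. Reproduce the window.** The Table 6-2 footnote sets the target as months × 30.4375 days and the window limits as midpoints between adjacent targets.

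- Target: 36 × 30.4375 = 1095.75, so Day 1096.
- Start: the midpoint of 914 and 1096 is (914 + 1096)/2 = 1005, which closes Month 30, so Month 36 opens on Day 1006.
- End: the table has no Month 42. With a notional one at 42 × 30.4375 = 1278.375, the midpoint is (1096 + 1278.375)/2 = 1187.19, so Day 1187.

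All three agree with the table.

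**2. Study day of planned completion.** Three calendar years are 1095 days, or 1096 with a leap day. Day 1 is the first in-study dose, taken here as the enrollment day. The 3-year point is then 1 + 1095 = Day 1096, or 1 + 1096 = Day 1097.

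**3. Gap to the end of the window.**

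| End of planned follow-up | Study day | Days short of Day 1187 |
|---|---|---|
| 3-year point | 1096 or 1097 | 91 or 90 |
| 3-year point plus 28 days for adverse events | 1124 or 1125 | 63 or 62 |

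If the first in-study dose comes after enrollment, the 3-year point falls on an earlier study day and the gap widens. Starting from Day 1096, an assumed lag of 7 days gives 1187 − 1089 = 98, and 30 days gives 1187 − 1066 = 121.

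**4. Early discontinuers in the same window.** A last dose inside the Month 36 window but before the 3-year point falls on Days 1006 to 1095 (90 possible days) or 1006 to 1096 (91 possible days). With 90 days of follow-up, the latest contact is 1095 + 90 = Day 1185 or 1096 + 90 = Day 1186. Every case falls short of Day 1187. If 3 months is taken as 92 days, only a last dose on Day 1095 or later reaches it (1095 + 92 = 1187). These are counts of days, not patients.

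**5. What the sentence restricts.** Three things favour the missing counts: the denominator is already fixed in the preceding paragraph, the condition directly follows the missing counts, and neither SAP 8.2.1.3 nor Protocol 6.5.1.1 has such a condition. The sentence's own general wording is the evidence for a table-wide filter. SAP 8.3 shows that the SAP can be explicit: for its therapy-pattern summaries it names the summary that its inclusion rule restricts. The description of follow-up time in SAP 4.2.1 does not settle the matter, because time in the study for a completer is also about 3 years.

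**The case against.** The strongest reply is that the proportion's denominator is already defined, and that reading the later sentence as a table-wide filter would defeat a table in which Month 36 is listed for presentation. That is a good argument, and it makes the missing-counts reading the likelier one. It does not rescue the missing count, which the condition as written still distorts at Month 36.

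A second reply is that follow-up need not stop at Day 1096 or 1097. The After Month 36 window foresees on-treatment data past Day 1187, no visit schedule is imposed, and Protocol 3.4.1.1 follows patients who stop because of an adverse event until resolution if that takes longer than 3 months. This stands: some patients may satisfy the condition. None of it is an exception for completers on plan.

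A third reply is that SAP 4.1 already promises counts of missing values in general, and that SAP 8.2.1.2 covers Month 36 mUFC ("For each time window (Month 1, 3, 6, 9, 12, 18, 24, 30, 36), observed values" and changes) without the condition. This limits the damage. It does not tell the programmer whom to count in the table of 8.2.1.1.

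A reader might infer that the Month 36 proportion will be empty, or that it is biased. The documents do not support that: it needs the less likely reading, and it also needs no patient to be seen beyond plan.

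**Conclusion.** The point holds as a minor drafting defect. A patient who completes 3 years exactly to plan fails the stated condition at Month 36 by 90 to 91 days, or 62 to 63 days if the adverse event follow-up counts, and no passage exempts that patient. The likely consequence is that on-plan completers without a Month 36 mUFC are missing from the missing count. Their loss from the proportion itself is possible but less likely.

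The day counts assume that the first in-study dose falls on the enrollment day and, for early discontinuers, that 3 months means 90 days. How many patients are affected cannot be known from the documents, because it depends on when last visits occur. The endpoint is descriptive and no formal hypothesis testing is planned, so no confirmatory conclusion is at risk.

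**What to change.** Add to SAP 8.2.1.1:

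1. The proportion in each window uses every patient with an on-treatment mUFC and ULN in that window.
2. The follow-up condition applies only to the missing-value counts. A plausible purpose, not stated in the SAP, is to keep windows still open at an interim cut-off from being counted as missing.
3. Completing the 3-year observation period satisfies the condition at Month 36.

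The cost is two or three sentences and a matching check in the table program. No new data and no new analysis are needed.
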